ASL images were motion corrected using the ASL MRI MoCo Method (Wang 2012). An additional motion correction and signal outlier filtering step was included (Tan et al 2009) to account for excessive motion and corruptive signal fluctuations. ASL images were converted into absolute CBF units according to the general kinetic model. The 8 CBF images were concatenated, intensity normalized, and then smoothed with a 9mm full-width half maximum (FWHM) Gaussian kernel. The images were spatially normalized to the MNI (Montreal Neurologic Institute) standard space using a 12-parameter affine transformation and then a nonlinear transformation. Additionally, a global white matter value was calculated for each CBF image by

extracting average white matter values from FSL's MNI152 white matter mask. The global white matter value was included in statistical models as a nuisance regressor.

Statistical Approach for fMRI: A group one-sample t-test ($n = 29$) was used to determine whole-brain, pain-related regions. The two Warm+No Meditation scans were subtracted from the two Noxious+No Meditation scans and then averaged. This average residual value per subject was used as the dependent measure included in the one-sample t-test.

Multiple regression analyses investigated the relationship between pain intensity/unpleasantness ratings and CBF during the Noxious condition. The 1st regressor consisted of the mean difference between the 2 Noxious+no Meditation scans vs Noxious+Meditation scans. The 2nd regressor included the percent change in subjects' pain intensity ratings from the Noxious+no Meditation to the Noxious+Meditation scans. The 3rd regressor included the percent change in the subjects' pain unpleasantness ratings from the Noxious+no Meditation to the Noxious+Meditation scans. All 3 regressors were orthogonalized to each other.

Because this was a proof-of-concept pilot mechanistic trial with a limited sample size, we set voxelwise threshold to 2.3, cluster corrected at $p=0.05$ (Worsley et al., 1992), in line with previous meditation-based imaging studies of similar size (Zeidan et al., 2015).

d. Early stopping rules.

We will report all adverse events and evaluate on a case-by-case basis whether the occurrence of a particular adverse event has implications for discontinuing the study to ensure participant safety and well-being.

8. Risks

a. Medical risks, listing all procedures, their major and minor risks and expected frequency.

Interventions. **Mindful breathing (MB)** is a basic mindfulness practice centered on maintaining non-reactive attention to breath in the present moment. Participants will be instructed to focus on breath sensations and practice non-judgmental awareness of disruptive internal milieu. No other mindfulness strategies will be instructed (e.g., loving kindness, yoga). **Savoring (SAV)** is a positive psychology practice designed to elicit positive emotions through attentional focus on a positive emotional experience. The proposed study will use a protocol adapted from Seligman et al.'s prior positive psychology interventions.¹¹⁵ No mindfulness strategies will be instructed (e.g., focused breathing, non-judgmental awareness of disruptive thoughts). **Sham MB** will be used as a control intervention based on protocols from previous research. Specifically, participants will be instructed to close their eyes and take a deep breath every 2-3 minutes while meditating. Individuals' posture, the intervention room, facilitator, and time spent providing instructions will be consistent with the MB condition.

Associated Risks. **MB, Sham MB, and SAV:** Mild risks are associated with MB, Sham MB, and SAV. First, participants might experience increased somatic focus, which may initially cause heightened attention to clinical pain sensations that are very likely to resolve with distraction. Further, there is a slight chance that participants will experience increased frustration during initial training sessions while trying to maintain focus on breath sensations and/or positive emotional memories.

Quantitative Sensory Testing (QST). QST is a non-invasive, systematic method of measuring individuals' pain sensitivity using a variety of noxious stimuli (e.g., thermal, mechanical, cold pressor).

Associated Risks. Participants will likely find the QST procedures uncomfortable during administration of stimuli for a brief period of time. This effect is expected to be transient and to produce only mild levels of discomfort. There is a slight risk that sensitive individuals may experience temporary redness to the stimulated location on the skin.

MRI: During the MRI scan, participants will be exposed to a strong magnetic field. No long-term negative side effects have been observed from this type of study. However, the MRI equipment is very noisy, and participants will be given earplugs to reduce this effect. Being in an MRI scanner can cause claustrophobia in some people. For some people, MRI may be unsafe.

Questionnaires. Broadly, questionnaires will measure domains of emotional functioning, clinical pain severity, clinical pain interference, fatigue, and adeptness with mindfulness skills.

Associated Risks. A minor risk associated with completing questionnaires is that participants may become fatigued or bored. There is a slight risk that questions involving mental health might lead to increased emotional distress in sensitive participants.

Urine Sample: A urine sample will be collected at the screening phase of each study visit to exclude individuals who screen positively for pregnancy or recreational drug use.

Associated Risks. There are no known risks to collecting a urine sample. However, participants may feel psychological stress or anxiety due to the outcome of tests, such as if urine pregnancy test is positive.

Collection of Private Identifiable Information. All data as described above will be de-identified with private identifying information located in a separate, protected file. The private identifiable information that we will collect includes specific diagnostic verification from medical record review, birth date, and contact information.

Associated Risks. As in all human subjects protocols, there is a mild risk of breach of confidentiality of private identifiable information, which could inadvertently cause distress to the individual participant.

b. Steps taken to minimize the risks.

Planned Strategies for Minimizing Potential Risks. All research personnel will be fully trained in the protection of human subjects as required by the Johns Hopkins School of Medicine. Any modification to the protocol, consent form, or study forms will be submitted to the Johns Hopkins IRB for review. If any participant is in need of emergent medical or mental health care, we will escort the participant directly to the emergency room, located within 50 yards of our lab. Participants will be informed of all study risks during the informed consent process. We will ensure that participants are aware of their right to stop any procedure they find too uncomfortable. Specific protections against risks are outlined below.

Interventions. The PI is a licensed clinical psychologist and will be available to meet with any interested participant who experiences emotional or somatic discomfort, or excessive frustration, during the interventions.

Quantitative Sensory Testing (QST). First, participants will be informed of the QST procedure during the informed consent and will be able to make an informed decision regarding their study participation. Second, we will use standardized QST procedures with which we have extensive experience, and that are known to produce transient effects that are unlikely to produce any residual pain. Third, the equipment used for thermal stimuli has an upper limit (51°C) at which the system will automatically shut down to prevent tissue injury. Fourth, participants will be informed that they can revoke their consent to participate in the pain testing at any time without penalty. Fifth, the

participants will be monitored throughout the duration of their outpatient visits by study staff and will have access to medical care and concomitant medications to treat residual pain, if necessary. Finally, QST equipment is regularly tested to ensure proper functioning.

MRI: We will perform a preliminary screening before the participant is enrolled in the study to ensure there are no obvious contraindications for MRI, such as the presence of a pacemaker or claustrophobia. On the day of the MRI scan, before the participant undergoes MRI we will perform a standardized screening to ensure that it is safe for the participant to undergo MRI. In the event that participants become claustrophobic, they can press an emergency buzzer and we will remove them from the scanner. The scanner has an intercom system so we will always be in contact with the participants and they can request to be removed from the scanner.

Questionnaires. Participants will be offered breaks while completing questionnaires if fatigued or bored. Participants will also be instructed that they do not need to disclose any information that may be too uncomfortable and of their right to stop the questionnaire. If a participant experiences psychological distress related to completing questionnaires, a study clinical psychologist (licensed in the state of Maryland) will be available to intervene as necessary.

Urine Sample: Strict confidentiality of the sample and results will be maintained. Urine pregnancy testing results will be shared with participants. A licensed study clinical psychologist or the study physician will discuss any positive pregnancy test results directly with the participant and make appropriate referrals or recommendations for further medical care as warranted.

Protection of Private Identifiable Information/Confidentiality. Every effort will be made to prevent a breach of confidentiality. In accordance with HIPAA regulations, all potential participants will be fully informed of their rights pertaining to disclosure of patient health information. The data will be managed and protected as follows: (1) participants will be assigned a code number and only the code number will be used to identify the neuroimages (at UMB) and urine results, standardized questionnaire information, and QST data; (2) a unique, password-protected electronic file will be created for participants' protected health information and identification number that will be stored in a separate location on a secure server from study-specific data; (3) written documents concerning the studies will be kept in locked cabinets with the key maintained in a secure location within the research center; (4) data will be housed on secure workstations connected to servers behind either a JHU (behavioral data) or UMB (neuroimaging data) firewall that are accessible by study members who hold authenticated logins and passwords, and data will be backed up by the PI and HIPAA-trained research assistant regularly onto an encrypted hard drive. All personnel will have undergone training/certification for handling such materials as required by the NIH and Johns Hopkins University. Only summaries of group data, without any individual identification, will be reported in any publications or presentations.

c. Plan for reporting unanticipated problems or study deviations.

All adverse events will be reported to the IRB and other relevant agencies as required. The Principal Investigator and Co-investigators are responsible for reporting such events.

At each study visit, an electronic adverse event tracking form (e.g., in RedCap) will be used to record and track any emergent adverse events. A staff entry of an adverse event will trigger an email to the study team and alert the PI to review and complete the adverse event tracking form, grading the severity of the AE (1-mild, 2-moderate, 3-severe), and determining the relatedness of the event to the research study. This form is also used in identifying when the symptom resolves and logging actions taken. The form includes the definition of a "Serious Adverse Event (SAE)." Should the AE be determined to meet the criteria of a SAE, the SAE tracking form opens automatically to capture that information. These forms will be maintained during the entire course of participation.

The PI will review AE tracking forms for identification of whether an AE is an unanticipated problem based on OHRP criteria. To make this determination, we will follow the OHRP algorithm, which considers whether the event is unexpected in nature, severity, or frequency. We will also consider whether the event is rated as related or possibly related to the study. Based on this information the PI will determine whether the AE suggests that the research places subjects or others at a greater risk of physical or psychological harm than previously known or recognized. AEs determined to be an unanticipated problem will be reported as described below.

Adverse events meeting criteria as **serious adverse events (SAEs)** will be reported as soon as possible and within 48 hours to IRB. The AE tracking form will automatically alert all study team members of the occurrence of an adverse event. The PI is notified directly via email to complete the AE report to facilitate immediate determination of the severity of the adverse event and whether it meets the criteria of an SAE. An AE determined to be an **unanticipated problem**, but not meeting the definition of an SAE will be reported promptly to IRB according to established IRB guidelines. All AEs, regardless of whether they are “serious” or an “unanticipated problem,” will be reported in summary form regularly at monthly intervals to the entire study team and to IRB annually at the time of continuing review. Adverse event forms will be housed electronically (e.g., in RedCap) with all related information for seamless tracking, reporting and follow up. The participant’s name will not be attached to any data and all information related to the adverse event will be identified by participant number.

Similarly, all protocol deviations will be tracked in the study database. Protocol deviations will be categorized according to type (e.g. Missing data, study visit out of window, incomplete questionnaires, etc) and reviewed at bi-monthly project meetings. All protocol deviations will be reported annually to the IRB at time of continuing review.

d. Legal risks such as the risks that would be associated with breach of confidentiality.

Although there is always a small risk that confidentiality will be breached, we believe this risk to be very minimal with the current study.

e. Financial risks to the participants.

None.

9. Benefits

a. Description of the probable benefits for the participant and for society.

All participants will receive an intervention from which they may benefit, including the sham MB intervention, which is an active deep breathing intervention. The knowledge to be gained regarding the effects of mindfulness and savoring on pain-related brain function in RA will yield potential benefits to those who have RA, and to society as a whole.

10. Payment and Remuneration

a. Detail compensation for participants including possible total compensation, proposed bonus, and any proposed reductions or penalties for not completing the protocol.

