Study Protocol for Meditation Effects on Brain Function in Rheumatoid Arthritis

NCT03975595

July 28, 2022

JHM IRB - eForm A – Protocol

- Use the section headings to write the JHM IRB eForm A, inserting the appropriate material in each. If a section is not applicable, leave heading in and insert N/A.
- When submitting JHM IRB eForm A (new or revised), enter the date submitted to the field at the top of JHM IRB eForm A.

1. Abstract

- a. Provide no more than a one page research abstract briefly stating the problem, the research hypothesis, and the importance of the research.

The purpose of this study is to determine and optimize the neural mechanisms supporting mindfulness-based pain relief in rheumatoid arthritis (RA) patients. The scientific premise is that rheumatoid arthritis (RA) patients' use of an elemental mindfulness meditation practice—mindful breathing (MB)—and a positive emotion generative practice—savoring (SAV)—during noxious thermal stimulation will increase activation in the corticostriatal circuits. The corticostriatal circuits are attractive neural mechanisms of the putative benefits of mindfulness for RA because directly support cognitive appraisals of aversive stimuli and reward valuation, which are behavioral targets of our interventions. Target corticostriatal regions include the lateral orbitofrontal cortex (IOFC) and putamen, which support top-down control of attention and emotional appraisals, and the ventromedial prefrontal cortex (vmPFC) and nucleus accumbens (NAc), which support positive emotion regulation and reward appraisals. The behavioral output of the corticostriatal circuits is especially relevant for patients with RA, due to the flaring, unpredictable nature of RA pain and the importance of positive emotional function to RA pain coping. Our original plan was to randomize RA patients to a brief 4-session (20 minutes each) course of MB (n=20), SAV (n=20), or a sham MB control (n=20). To adjust to the ongoing COVID-19 pandemic, we will stop randomizing to MB and only randomize to SAV or sham MB. At post-intervention, participants will undergo functional MRI (fMRI) using a perfusion-based arterial spin labeling (ASL) technique during noxious thermal stimulation to determine if MB and SAV are associated with corticostriatal activation when compared to Sham MB.

2. Objectives (include all primary and secondary objectives)

- 1) Determine if MB activates corticostriatal circuits during noxious stimulation.

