- 2) Determine if SAV activates corticostriatal circuits during noxious stimulation.
- 3) Determine if MB and/or SAV evidence stronger activation of corticostriatal circuits during noxious stimulation.

3. Background (briefly describe pre-clinical and clinical data, current experience with procedures, drug or device, and any other relevant information to justify the research)

RA is a chronic systemic inflammatory disorder that is characterized by variable levels of pain that range from mild to debilitating and can flare unpredictably. RA affects approximately 3 million individuals in the United States, accounting for an annual cost of 46.7 billion dollars.^{1,2} Disease modifying anti-rheumatic drugs (DMARDs) are commonly used to manage RA symptoms by blocking pro-inflammatory cytokines, but symptom profiles and response to treatment vary substantially between patients³; up to 25%

of those receiving DMARDs show little or no improvement^{4,5}, and 20-40% of patients report chronic widespread pain that is poorly responsive to treatment.⁶⁻⁸ Additionally, pain flares can be unpredictable, varying substantially within patients^{9,10}, even during the course of pharmacotherapy.¹¹⁻¹³ Given these considerations, there has long been a keen interest in the use of non-pharmacological treatments as an adjunct to traditional pharmacotherapy to help patients “self-manage” pain and other RA symptoms.¹⁴⁻¹⁶ Indeed, research shows that modifiable psychological factors critically influence adaptation to RA.¹⁷

Mindfulness-based therapies are attractive candidate nonpharmacological interventions for the treatment of RA for several reasons. First, they attenuate the experience of acute pain at behavioral and corresponding neurobiological levels.^{18,19} Second, they are premised on sustaining non-reactive attention to the breath in the present moment²⁰, and are therefore well-suited to promote acceptance-based appraisals of *real-time* internal and external experiences.²¹ This type of skill is especially relevant to RA, given the flaring nature of RA pain.¹²⁻¹⁴ Third, they are associated with reductions in anxiety and depression²²⁻²⁴, which are common RA comorbidities that complicate treatment.^{25,26}

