Second, we propose that SAV will engage different aspects of the corticostriatal circuits. SAV is traditionally a non-mindful cognitive strategy that promotes positive emotions through focused attention on pleasurable thoughts or sensory experiences.⁶⁰⁻⁶² Importantly, positive emotions are linked to activity within two other critical corticostriatal structures: the ventromedial prefrontal cortex (vmPFC), which is associated with the regulation of positive emotions⁶³⁻⁶⁶, and the nucleus accumbens (NAc), which is associated with reward valuation in human and animal studies.⁶⁷⁻⁶⁹ Indeed Speer et al.⁷⁰ showed that NAc and vmPFC function were significantly augmented during a basic savoring task, and NAc function correlated with the experience of positive emotions.

We plan to use these data to inform a follow-up study in which we combine MB and SAV and determine whether the combination optimizes the engagement of corticostriatal circuits during noxious stimulation.

4. Study Procedures

- a. Study design, including the sequence and timing of study procedures (distinguish research procedures from those that are part of routine care).

Overview of Study

We aim to demonstrate that MB promotes lOFC and putamen activation and SAV promotes NAc and vmPFC activation during noxious thermal stimulation among RA patients. We will execute a randomized controlled trial (RCT) comparing two arms: SAV, and sham MB in 40 RA patients (n = 20 per group). Originally, we also randomized participants to a third arm (MB). However, due to the disruption of the COVID-19 pandemic, we will no longer randomize to MB, in order to optimize our ability to complete the project on budget. The screening and intervention sessions will take place either via secure remote video conference (e.g., Zoom), or at Johns Hopkins Bayview Medical Center, as dictated by fluid laboratory density needs and participant safety precautions. There will also be a post-intervention fMRI task, which will take place at University of Maryland-Baltimore (UMB). The fMRI visit is the only that will take place at UMB.

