Mixed effects modeling will be used as the primary analytic strategy for the primary outcomes. In our group therapy RCT design, mixed effects models permit the modeling of cohort-level random effects, as well as heterogeneous variance/covariance matrices to account for potential alpha inflation due to cohort-level clustering. We will test regional signal change in each ROI using mixed effects models examining within-person main effects of thermal stimulus (HEAT; i.e., painful vs. warm) and skill practice (PRACTICE; i.e., rest vs. active practice in the scanner during delivery of thermal stimuli), and the between-person main effect of intervention condition (CONDITION; i.e., MB vs. Sham MB vs. SAV), as well as their requisite 2-way and 3-way interactions. Thus, the HEAT X PRACTICE X CONDITION interaction will test the extent to which CBF in each a priori corticostriatal region varies during the active practice of either Sham MB, or SAV, relative to rest. Planned comparisons will test each of the HEAT X PRACTICE 2-way interactions within intervention groups to aid in the interpretation of the 3-way interaction.

Updated Statistical Approach due to Covid-19

Due to COVID-19 restrictions, we had to drop one arm from the study (Mindful Breathing). As such, a new statistical analysis plan was developed that we detail in the next section.

fMRI Pre-Processing: Imaging analysis was conducted using Functional Magnetic Resonance Imaging of the Brain (FMRIB) Software Library (Center for FMRIB, University of Oxford, Oxford, UK) and ASL data processing toolbox. Five subjects were excluded from analysis due to detected image artifact or excessive motion. A total of 29 subjects (15 SAV group, 14 NMB) were included in the final imaging analysis. Subjects underwent 8 functional (ASL) runs during the MRI challenge session. The 8 ASL images that resulted from the runs represented combinations of two experimental conditions: Pain (nonpainful warm stimulus vs. noxious heat) and Practice (no meditation vs. meditation). These combinations occurred in the following order: 1. warm + no meditation; 2. noxious + no meditation; 3. warm + no meditation; 4. noxious + no meditation; 5. warm + meditation; 6. noxious + meditation; 7. warm + meditation; 8. noxious + meditation.

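### Objective 1 and the mindful-breathing part of Objective 3 outlived the arm they depend on, and the updated analysis plan states no savoring-versus-sham contrast for the question that remains

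*Combined protocol and SAP*

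**What the plan says.** The abstract reports that, because of the pandemic, "we will stop randomizing to MB and only randomize to SAV or sham MB". Section 4a (Overview of Study) repeats this, "due to the disruption of the COVID-19 pandemic, we will no longer randomize to MB", and describes the trial as "comparing two arms: SAV, and sham MB in 40 RA patients (n = 20 per group". Section 4a (Screening and Randomization) dates the change to July 2020.

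Other current text still treats MB as a live arm:

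- Section 2, Objective 1: "Determine if MB activates corticostriatal circuits during noxious stimulation".
- Section 2, Objective 3: "Determine if MB and/or SAV evidence stronger activation of corticostriatal circuits during noxious stimulation".
- Section 1, after the sentence that drops MB, gives the purpose of the scan as "to determine if MB and SAV are associated with corticostriatal activation when compared to Sham MB".
- Section 3 keeps the bolded hypothesis that MB raises lateral orbitofrontal (lOFC) and putamen activation above sham.
- Section 4a (Overview of Study) opens with the aim of showing that MB acts on lOFC and putamen, and SAV on nucleus accumbens (NAc) and ventromedial prefrontal cortex (vmPFC).
- Section 7c (Data Analysis) includes "the between-person main effect of intervention condition (CONDITION; i.e., MB vs. Sham MB vs. SAV").

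Objective 2, "Determine if SAV activates corticostriatal circuits during noxious stimulation", does not involve MB. Section 7c (Updated Statistical Approach due to Covid-19) says that a new analysis plan was written because MB was dropped. It reports 29 analysed subjects, 15 SAV and 14 NMB. NMB is not defined, but it is the only other group listed.

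**The concern.** The arms were amended but the questions were not. A reader who takes Section 2 at face value expects a conclusion on MB, and the randomised comparison now running cannot supply one.

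The mismatch also hides a second gap. Because the objectives were never restated for two arms, the updated plan was written without naming the comparison that is now the trial's main question, SAV against sham MB. At stake is whether the report has a defined primary between-group result, or only pooled findings set beside objectives that they do not address.

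**Working it through.** **1. The plan's own sample size.** Section 7c targets 20 per group and 40 in total. 2 × 20 = 40, so the target matches two arms. The three-arm design in the abstract would be 3 × 20 = 60. The sample size was updated and leaves no MB allocation.

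**2. The imaging set.** 15 SAV + 14 NMB = 29, so 29 − 15 − 14 = 0 for MB. An MB contrast cannot be estimated in this set. The number randomised to MB before July 2020 is not given.

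**3. Objectives against arms.**

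| Objective | Needs MB? | Answerable with SAV and sham MB? |
|---|---|---|
| 1 (MB) | Yes | No |
| 2 (SAV) | No | Yes |
| 3, read as MB versus SAV | Yes | No |
| 3, read as each practice versus sham | Only for the MB part | Yes, for the SAV part |

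Objective 3 names no comparator, so both readings are open. One objective is lost wholly and one in part.

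**4. The mixed model.** HEAT and PRACTICE have two levels each. With three conditions the three-way interaction has (2−1)(2−1)(3−1) = 2 degrees of freedom. With SAV and sham MB only it has (2−1)(2−1)(2−1) = 1. The sentence after the CONDITION factor describes that interaction for sham MB or SAV alone, so the section was only partly edited.

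**5. The updated plan against the remaining question.** Statistical Approach for fMRI gives two analyses. The first is a one-sample t-test on all 29, using noxious minus warm scans without meditation. The second is a set of multiple regressions with three regressors: the noxious scan difference with and without meditation, and the percent changes in pain intensity and in unpleasantness. Neither description contains a group term, a SAV-versus-sham contrast or an analysis by a priori region.

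**6. What the power statement covers.** The figure of 17 per group came from simulation on an MB-versus-sham data set. No effect size or standard deviation is given, so it cannot be reproduced, and it does not concern SAV. As an illustration only, assume a two-sample comparison with exactly 80% power at 17 per group:

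- Two-sided 0.05: d = (1.960 + 0.842) × √(2/17) = 0.96 by the normal approximation, or 0.99 by the t-test. With d = 0.99, t-test power is about 86% at 20/20 and 73% at 15/14.
- Two-sided 0.0125 (assuming Bonferroni over four regions): d = 1.21 by the t-test. Power is about 88% at 20/20 and 71% at 15/14.

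These figures apply to SAV versus sham only if its effect equals the assumed MB effect, which the documents do not claim.

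**The case against.** The strongest reply is that this is leftover wording. The loss of MB is stated openly in the abstract, the overview, the randomisation text and Section 7c. The sample size was reset to two arms, and the document says that a new plan replaced the three-arm one. Much of this stands, and it rules out several stronger readings that a reader might infer:

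- *Two of the three objectives are lost.* Not supported. The and/or wording of Objective 3 leaves its SAV part answerable against sham MB.
- *The primary model requires MB and tests an empty arm on 2 degrees of freedom.* Not supported. An empty level cannot be fitted, the model runs with two levels, and the next sentence already names only two groups.
- *lOFC and putamen have no data, or serve only MB.* Not supported. Perfusion images exist for all 29. The abstract lists all four regions as targets, and Section 7c tests each a priori region under sham MB or SAV. The overview does tie the SAV-specific hypothesis to NAc and vmPFC.
- *Error is spent on regions without a hypothesis.* Not supported. No alpha is allocated across regions, so removing two would free none.
- *Pooled results will pass for evidence on mindfulness.* Speculative. The one explicitly pooled test uses scans without meditation.

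The reply does not cover two things. Section 2 still states an objective that the trial cannot meet, and the replacement plan does not state the comparison that the trial can make.

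**Conclusion.** The point holds as an unresolved inconsistency with one analytic consequence. Objective 1, the MB part of Objective 3, the abstract and overview aims, the MB hypothesis and the CONDITION factor were not revised after July 2020. Neither the two-arm design nor the 29-person imaging set can answer Objective 1 or any MB comparison. Objective 2 and the SAV part of Objective 3 remain answerable by design, but the updated plan states no SAV-versus-sham contrast for them.

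This rests on two readings: that NMB denotes the sham arm, and that the updated section replaces the mixed model, as its introduction indicates. If the mixed model is still in force, a two-level interaction supplies the contrast, but the document should then say so. The finding does not invalidate the comparison of SAV with sham MB.

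**What to change.** - Mark Objective 1 and the MB hypothesis as discontinued, with the date and reason, and draw no conclusion on MB.
- Restate Objective 3 and the abstract and overview aims as SAV versus sham MB.
- Make CONDITION two-level. Carry the SAV-versus-sham HEAT × PRACTICE × CONDITION contrast into the updated plan as the primary comparison in the a priori corticostriatal regions.
- Date that contrast and label it as specified after the arm was dropped and after the analyses that the section already reports in the past tense.
- Keep all four a priori regions, noting that the SAV-specific hypothesis concerns NAc and vmPFC. Demoting lOFC and putamen now would be a further post hoc change.
- State how many participants were randomised to MB before July 2020 and report them descriptively only. Define NMB.

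The cost is amendment wording and one analysis of data already in hand. The downside is a narrower stated scope and a primary contrast that cannot be presented as prespecified.
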